5. ASSESSMENT OF SAFETY

5.1 SAFETY PLAN

The safety plan for patients in this study is based on nonclinical and clinical experience with GDC-0853 in completed and ongoing studies as well as published literature on

GDC-0853—Genentech, Inc.

other BTK inhibitors. The important potential safety risks for GDC-0853 are outlined below. Please refer to the GDC-0853 Investigator's Brochure for a complete summary of safety information.

Several measures will be taken to ensure the safety of the patients participating in this study. Eligibility criteria in both the controlled and open-label studies have been designed to exclude patients at a higher risk for potential toxicities. Patients will undergo safety monitoring during the study, including monitoring of vital signs, physical examination, ECGs, and routine laboratory safety assessments (hematology, chemistry, and urinalysis) and assessment of the nature, frequency, and severity of adverse events. In addition, guidelines for managing potential adverse events, including criteria for treatment interruption or discontinuation, dose reduction, and enhanced safety reporting are provided below.

Dose reduction from 200 mg BID to 200 mg QD for safety events is permitted for specific events as detailed in Table 3 of Section 5.1.2. For adverse events not listed in the table where the investigator thinks a dose reduction may be indicated, please consult with the Medical Monitor.

5.1.1 Safety Plan for Potential Risks Associated with GDC-0853 5.1.1.1 Infections

GDC-0853 is a reversible inhibitor of BTK, and the degree to which GDC-0853 antagonism of BTK signaling may suppress immune activity is unknown. On the basis of patients with XLA, a primary immunodeficiency of B cells and immunoglobulin production, it is anticipated that inhibitors of BTK may raise the risk for certain bacterial infections (Lederman and Winkelstein 1985; Broides et al 2006), enteroviral infections (Misbah et al. 1992; Ziegner et al. 2002), intestinal infections with giardia and campylobacter species (Winkelstein et al. 2006; van den Bruele et al. 2010), or other opportunistic infections, which are cleared primarily by B-cell adaptive immune responses. This risk is likely independent of sex for patients exogenously administered GDC-0853.

Effects on lymphocytes and immunoglobulins in rats and dogs were reversible and considered to be related to pharmacological activity involving BTK inhibition. See Section 1.2.2 for related primary nonclinical toxicity findings and the GDC-0853 Investigator's Brochure for further details.

To date, no immune-challenge experiments (e.g., T-dependent antigen response test) have been conducted in animals. It is not known whether these effects on B cells and IgG concentrations in animals will translate to humans or whether such changes would have functional or deleterious impact on immune function.

Infections, including pneumonia and fatal influenza infections, have occurred in patients with B-cell malignancies treated with GDC-0853. In studies with healthy subjects with

single doses and with dosing for 14 days, self-limited Grade 1 events of nasopharyngitis were reported but did not lead to any change in study drug dosing. One subject had asymptomatic bacteriuria, which resolved while study drug dosing continued.

Total Ig, IgG, IgM, IgA, and IgE concentrations will be measured regularly throughout the study. All patients in the study should be monitored for fever and potential infectious complications, including opportunistic infections and tuberculosis, and should be evaluated promptly. Physicians or a health care provider should give patients advice to prevent potential transmission of and exposure to endemic infections according to local or Centers for Disease Control and Prevention guidelines. Patients should be advised to seek immediate medical attention if they develop signs and symptoms suggestive of an infection. All infections occurring during the study, including but not limited to respiratory infections, cutaneous infections, urinary tract infections, systemic viral infections, and episodes of suspicious or febrile diarrhea, should be evaluated using serology or PCR if available and cultured if feasible and any identified organisms noted in the eCRF. Any serious infection, infection requiring IV antimicrobials (i.e., any Grade 3 infection) or any opportunistic infection is considered as an adverse event of special interest and should be reported to the Sponsor in an expedited manner as outlined in Section 5.2.3.

Guidelines for management of GDC-0853 in the event that infections are observed in patients are provided in Table 3.

Please also refer to the GDC-0853 Investigator's Brochure for further details.

5.1.1.2 Vaccinations

The effect of GDC-0853 upon the efficacy of vaccinations is unknown. It is recommended that appropriate vaccinations per ACR (Singh 2016) or European League Against Rheumatism (EULAR; van Assen 2010) recommendations or local guidelines be up to date before entry into the blinded study. Immunization with a live or attenuated vaccine is prohibited for the duration of study participation, including the 8-week follow-up period after the administration of the last dose of GDC-0853.

In addition, current routine household contact with children or others who have been vaccinated with live vaccine components may pose a risk to the patient during study treatment with GDC-0853. Some of these vaccines include varicella ("chickenpox") vaccine, oral polio vaccine, and the inhaled flu vaccine. Following vaccination with live component vaccines, the virus may be shed in bodily fluids, including stool, and there is a potential risk that the virus may be transmitted to the patient.

General guidelines for immunosuppressed patients suggest that exposure to vaccinated individuals should be avoided following vaccination with these vaccines for the stated time periods:

Varicella or attenuated typhoid fever vaccination for 4 weeks following vaccination;

- Oral polio vaccination for 6 weeks following vaccination;
- Attenuated rotavirus vaccine for 10 days following vaccination;
- FluMist[®] (inhaled flu vaccine) for 1 week following vaccination.

Please refer to the GDC-0853 Investigator's Brochure for further details.

5.1.1.3 Bleeding

No decrease in platelets, changes in coagulation parameters, or bleeding events were observed in nonclinical studies with GDC-0853. Bleeding events, including non–serious CTCAE Grade 1 bruising and serious Grade ≥3 GI bleeding, have been reported in patients with hematological malignancies treated with GDC-0853 in Study GO29089. The GI bleeding events have not been dose related, and the events occurred in patients who were taking concomitant NSAIDs and who had a history of gastroesophageal or peptic ulcer disease. The impact of BTK inhibition as a potential risk factor for bleeding is unknown. BTK is expressed in platelets and is involved in platelet function via GPVI/Collagen receptor signaling and GP1b receptor signaling. Platelets from patients with XLA, a genetic deficiency of BTK, demonstrate decreased activation in response to submaximal collagen stimulation but normal response to thrombin; clinically, there is no reported bleeding propensity in patients with XLA.

Bruising or bleeding events related to GDC-0853 have not been reported in healthy subjects.

It is unknown whether GDC-0853 will increase the risk of bleeding in patients, especially in those receiving anti-platelet or anti-coagulant therapies. Patients should be advised to seek immediate medical attention if they develop signs and symptoms suggestive of clinically significant bleeding.

Several risk factors, including patient age, co-morbidities, concurrent medications, prior medical history, and *Helicobacter pylori* infection, have been demonstrated in a variety of studies to increase the risk of NSAID-related GI injury (Lanza et al. 2009). It is unknown whether GDC-0853 will increase the risk of bleeding in patients receiving NSAIDs. Therefore, in order to prevent NSAID-related GI complications in high-risk patients, concomitant use of PPIs should be considered (Scheiman 2008) and used according to local or recognized guidelines (e.g., ACCF/ACG/AHA 2008 Expert Consensus Document).

Patients at high risk for NSAID-related GI toxicity include:

- Patients using both aspirin and an NSAID
- Patients with a history of ulcer disease

Patients with one or more of the following:

Age ≥60years

High-dose NSAID use

Concurrent corticosteroid use

Dyspepsia or gastroesophageal reflux disease symptoms

Any bleeding event Grade 2 or above is considered an adverse event of special interest and should be reported to the sponsor in an expedited manner as outlined in Section 5.2.3.

Guidelines for management of GDC-0853 in the event that bleeding is observed in patients are provided in Table 3. Please refer to the GDC-0853 Investigator's Brochure for further details.

5.1.1.4 Cytopenias

Cytopenias have been observed in patients with hematological malignancies who received GDC-0853, including neutropenia, anemia, and thrombocytopenia; events have been monitorable and clinically manageable (see the GDC-0853 Investigator's Brochure for further details).

Patients should be monitored regularly with hematology laboratory evaluations as outlined in the schedule of assessments and should receive appropriate supportive care as clinically indicated. Patients should be advised to seek immediate medical attention if they develop signs and symptoms suggestive of cytopenias (e.g., persistent fever, bruising, bleeding, pallor).

Guidelines for the management of GDC-0853 in the event of cytopenias in patients are provided in Table 3. Please refer to the GDC-0853 Investigator's Brochure for further details.

5.1.1.5 Gastrointestinal Effects

Body weight gain and food consumption changes have been observed in animals, including nonsignificant increases in male Wistar-Han rats administered ≥ 2 mg/kg/day (4.3 $\mu M \bullet h$) for 6 months, and significant reductions in rats administered 100 mg/kg/day (1438 $\mu M \bullet h$) and dogs administered 25 mg/kg (180 $\mu M \bullet h$) for 4 weeks. These effects on body weight gain and food consumption were reversible following discontinuation of GDC-0853 dosing.

Grade 1 diarrhea, nausea, and abdominal pain have been reported in in patients with B-cell malignancies; however, the events have resolved and have not led to study drug discontinuation. Healthy subjects in the MAD Study GA29347 reported events of mild self-limited nausea.

Throughout the study, patients will be monitored for GI effects.

Guidelines for management GDC-0853 in the event of GI side effects in patients are provided in Table 3. Please refer to the GDC-0853 Investigator's Brochure for further details.

5.1.1.6 Hepatotoxicity

Evidence of hepatobiliary injury was observed in animals administered relatively high doses of GDC-0853 in repeat-dose toxicity studies. Dose-dependent increases in ALT, AST, and/or bilirubin have been observed in rats administered ≥ 6 mg/kg/day ($\geq 17~\mu M \cdot h$) and dogs administered ≥ 10 mg/kg/day ($\geq 36~\mu M \cdot h$) with corresponding microscopic changes in the liver of dogs administered 25 mg/kg/day (180 $\mu M \cdot h$). The hepatotoxicity findings in dogs were associated with moribundity in two high-dose animals. The NOAEL for these findings was considered to be 10 mg/kg (36 $\mu M \cdot h$) in dogs, the most sensitive species, given the absence of GDC-0853-related hepatotoxicity at this dose when administered for 9 months. These findings were fully reversible and considered monitorable by changes in plasma transaminases and bilirubin that occurred at doses lower than those producing histopathology findings (see GDC-0853 Investigator's Brochure for further details).

In clinical studies to date including single dosing and multiple dosing for 14 days in healthy subjects and daily dosing for over 1 year in patients with hematological malignancies, there have been no adverse events of liver enzyme elevations nor trends toward elevations in laboratory evaluations.

As a safety risk—mitigation measure, to be eligible for the study, AST and/or ALT levels should be no more than 1.5×ULN and total bilirubin levels should be normal at Day 56 or Day 84 of Study GA29350 prior to entering Study GA30067 (see Section 4.1.2 for details). Safety monitoring for potential hepatotoxicity includes baseline and routine evaluations of AST/ALT and total bilirubin levels throughout the study as outlined in the schedule of assessments. The local prescribing information for MTX should also be consulted.

Laboratory results of AST or ALT elevations of Grade ≥ 3 (i.e., $> 5 \times$ ULN) are considered adverse events of special interest and should be reported to the Sponsor in an expedited manner as outlined in Section 5.2.3.

Guidelines for the management of GDC-0853 in the event of hepatotoxicity in patients are provided in Table 3. Please refer to the GDC-0853 Investigator's Brochure for further details.

5.1.1.7 Cardiovascular Effects

GDC-0853 is considered to have a low potential to cause QT interval prolongation or to directly affect other cardiovascular parameters, at therapeutic exposures. A minimal increase in corrected QT (QTc; 7 msec or 3%) interval was noted at 45 mg/kg in the single-dose, cardiovascular, safety, pharmacology study in telemetry-instrumented dogs.

Based on extrapolated/interpolated toxicokinetic data, the unbound C_{max} at 45 mg/kg (considered a NOAEL) and no-observable-effect level of 15 mg/kg

There have been no GDC-0853-related changes in ECG parameters in the 4-week or 9-month dog toxicity studies.

Analysis of ECG data from the SAD and MAD studies in healthy subjects did not demonstrate any significant increase in either QRS interval or QTcF intervals. However, cardiac safety will be evaluated in all patients at baseline and throughout the study, with routine monitoring of vital signs, including heart rate and blood pressure, collection of triplicate ECGs with PK-matched timepoints for cardiac interval analysis as outlined in the schedule of assessments, routine safety ECGs, and collection of adverse events (see Appendix 1).

Management of patients with sustained QTcF prolongation (QTcF that is >500 msec and/or >60 msec longer than the baseline value on at least two ECG measurements >30 minutes apart) should include close monitoring, with ECGs repeated at least hourly until two successive ECGs show resolution of the findings, correction of any electrolyte abnormalities, and possible discontinuation of other concomitant medications that are known to prolong the QT interval. Consultation with a cardiologist or electrophysiologist is recommended, to help in the management of such patients. The Medical Monitor should be notified as soon as possible (see Section 4.4.8).

Guidelines for management of GDC-0853 in the event of cardiovascular effects in patients are provided in Table 3. Please refer to the GDC-0853 Investigator's Brochure for further details.

5.1.1.8 Vascular Inflammation

Vascular inflammation (vasculitis) was observed in dogs administered GDC-0853 at \geq 10 mg/kg/day (\geq 56 μ M • h) in the 4-week toxicity study, and these changes were not completely reversed by the end of the 4-week recovery period. There was no consistent correlation with any clinical biomarkers. However, in the 9-month toxicity study in dogs, no GDC-0853-related vascular inflammation was observed up to the highest dose of 10 mg/kg/day (36 μ M •h), which is considered to be the NOAEL (AUC) for the canine vascular inflammation findings.

The translatability of

these findings to humans is unknown; however, Beagle dogs are susceptible to spontaneous development of polyarteritis syndrome (Snyder et al. 1995) and may be more sensitive to any drug-induced effects. Further, there are several examples of approved therapies for which there is no correlation between the finding of vasculitis in dogs or rats at clinically relevant exposures and adverse outcomes in patients (FDA 2011).

As a safety risk-mitigation measure, patients with a history of vasculitis, including RA-associated vasculitis, will be excluded from the study, and CBC, creatinine, and urinalysis will be monitored in all patients during the study. Study drug should be discontinued in any patient who develops an adverse event of vasculitis, and the patient should enter safety follow-up.

Guidelines for management of GDC-0853 in the event of vasculitis in patients are provided in Table 3. Please refer to the GDC-0853 Investigator's Brochure for further details.

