- Any major episode of infection requiring hospitalization or treatment with IV antibiotics during the Phase II Study GA29350
- Patients who developed a malignancy (with the exception of non-serious local and resectable basal or squamous cell carcinoma of the skin) during the Phase II Study GA29350
- 12-lead ECG on Day 84 in Study GA29350 that demonstrates clinically relevant abnormalities that may affect patient safety or interpretation of study results, including

QT interval corrected using Fridericia's formula (QTcF) > 440 msec demonstrated by at least two ECGs > 30 minutes apart

- Current treatment with medications that are well known to prolong the QT interval
- Laboratory values from the Day 56 visit of Study GA29350 (which may be repeated once at an unscheduled visit, if necessary) that meet the following criteria:

Creatinine > $1.5 \times ULN$ ALT or AST > $1.5 \times ULN$ Total bilirubin > ULNHemoglobin < 8.5 g/dLANC < $1.5 \times 10^9/L$ Platelet count < $100 \times 10^9/L$

End of Study

The end of this study is defined as the date when the last patient, last visit (LPLV) occurs or the date at which the last data point required for statistical analysis or safety follow-up is received from the last patient, whichever occurs later. LPLV is expected to occur approximately 60 weeks after the last patient is enrolled.

Length of Study

The maximum time in the study for a patient is 60 weeks, including treatment for 52 weeks and an 8-week safety follow-up period after the last dose of GDC-0853.

Investigational Medicinal Product

The investigational medicinal product (IMP) for this study is GDC-0853.

The GDC-0853 dose regimen is oral 200 mg BID. Patients will receive GDC-0853 approximately every 12 hours for 52 weeks. Patients should be directed to take one dose (a total of 4 tablets) BID (total of 8 tablets each day). On clinic visit days during the first 12 weeks of the study, patients should be instructed that the a.m. dose of GDC-0853 will be administered in the clinic, except for Day 1, since the last dose of GDC-0853 for Study GA29350 is the a.m. dose on Day 84 for all patients. For patients continuing into the OLE Study GA30067, the first open-label dose of GDC-0853 should be the p.m. dose (may be taken at home) on Day 84 (which is Day 1 of Study GA30067). After Week 12, GDC-0853 administration in the clinic is not required.

Non-Investigational Medicinal Products

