GDC-0853 is considered to have a low potential to cause QT interval prolongation or to directly affect other cardiovascular parameters at therapeutic exposures. A minimal increase in corrected QT (QTc; 7 msec or 3%) interval was noted at 45 mg/kg in the single-dose, cardiovascular, safety, pharmacology study in telemetry-instrumented dogs. Cardiac safety will be evaluated in all patients at baseline and throughout the study, with routine monitoring of vital signs, including heart rate and blood pressure, collection of ECGs, and reporting of cardiac adverse events.

Malignancy

The impact of BTK inhibition on the development of malignancies is not known; however, malignancies are considered a potential concern for all immunomodulatory agents. Patients with a history of cancer within 10 years before screening will be excluded *initially* from participation in Study GA29350 (and therefore from Study GA30067), except for basal or squamous cell carcinoma of the skin that has been excised and is considered cured and in situ carcinoma of the cervix treated with apparent success by curative therapy more than 1 year prior to screening. All malignancies are considered adverse events of special interest with expedited reporting requirements to the Sponsor.

Vasculitis

The risk to human safety based on toxicological findings of vascular inflammation in animal studies is uncertain. As a safety risk-mitigation measure, patients with a history of vasculitis, including RA associated vasculitis, will be excluded *initially* from Study GA29350 (and therefore from Study GA30067 and complete blood counts (CBCs), creatinine levels, and urinalysis findings will be monitored in all patients during both studies: Studies GA29350 and GA30067. Study drug should be discontinued in any patient who develops an adverse event of vasculitis, and the patient should enter the safety follow-up period.

Overall, GDC-0853 has been well tolerated in Phase I healthy subjects and in patients with hematological malignancies. On the basis of the compelling mechanism for BTK inhibition in RA, the risk-benefit ratio for this study is deemed acceptable. The long-term safety profile of GDC-0853 will be further characterized in this open-label Phase II study, and a robust safety monitoring plan that describes the potential risks for GDC-0853 and the risk-mitigation strategies to minimize risks for the patients in this trial is provided in Section 5.1.

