4.2.2.1 GDC-0853 Dose and Administration

The GDC-0853 dose regimen is oral 200 mg BID. Patients will receive GDC-0853 approximately every 12 hours for 52 weeks. Patients should be directed to take one dose (a total of 4 tablets) BID (total of 8 tablets each day). On clinic visit days during the first 12 weeks of the study, patients should be instructed that the a.m. dose of GDC-0853 will be administered in the clinic, except for Day 1, since the last dose of GDC-0853 for Study GA29350 is the a.m. dose on Day 84 for all patients. For patients continuing into the OLE Study GA30067, the first open-label dose of GDC-0853 should be the p.m. dose (may be taken at home) on Day 84 (which is Day 1 of Study GA30067). After Week 12, GDC-0853 administration in the clinic is not required.

A dose reduction of GDC-0853 for specific safety events is permitted (see Table 3). For a potential dose reduction for other adverse events not listed in the table, please consult the Medical Monitor. If dose reduction is indicated, the dose of GDC-0853 may be reduced from 200 mg BID to 200 mg QD. In this case, patients should be directed to take one dose (a total of 4 tablets) QD in the morning (total of 4 tablets each day).

Guidelines for dose reduction and treatment interruption or discontinuation are provided in Section 5.1.

GDC-0853 may be orally administered with or without food. The dates and times of the most recent prior meal, last dose of GDC-0853 (prior to clinic visit), and timing of GDC-0853 administration in clinic should be recorded at each clinic visit. In addition, any use of PPIs, H2-receptor antagonists (H2RAs), and/or other antacids (e.g., Maalox®, Pepto-Bismol®, Rolaids®) should be recorded as concomitant medications, including time and date of last administration. Administration of GDC-0853 should be staggered with antacid use (i.e., GDC-0853 should be taken 2 hours before or 2 hours after the antacid).

GDC-0853—Genentech, Inc. 51/Protocol GA30067, Version 2

At study visits, sufficient GDC-0853 tablets will be dispensed to complete dosing until the next scheduled visit. When GDC-0853 is administered at the site, it will be administered under supervision of study personnel, and the amount of GDC-0853 dispensed must be recorded.

4.2.2.2 *GDC-0853 Compliance*

The following measure will be taken to assess patient compliance with study drug: patients will be directed to bring any used and unused bottles to each visit.

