4.5.2 Study Treatment Discontinuation

Patients must discontinue study treatment if they experience any of the following:

- Pregnancy
- Anaphylaxis or other severe hypersensitivity reaction

- Malignancy (with the exception of non-serious local and resectable basal or squamous cell carcinoma of the skin)
- Any serious infection or infection requiring treatment with an IV antimicrobial agent
- Any prohibited medication as defined in Section 4.3
- Any Grade 3 or greater thrombocytopenia (National Cancer Institute Common Terminology Criteria for Adverse Events [NCI CTCAE v4.0])
- Any Grade 4 neutropenia (NCI CTCAE v4.0)
- Failure to achieve a 20% improvement in both SJC and TJC (relative to baseline values in Study GA29350) at Week 24

Patients who discontinue study treatment prematurely for the reasons listed above will be asked to return to the clinic for an early termination visit (see Section 4.5.1) followed by 8 weeks of safety follow-up.

The primary reason for study treatment discontinuation should be documented on the appropriate eCRF. Patients who discontinue study treatment prematurely will not be replaced.

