Grade 3: ANC 500–1000/mm ³	For the first occurrence of a Grade 3 neutrophil count decreased, withhold GDC-0853 and recheck the CBC in 7 days. If the neutrophil count has recovered to Grade 1 (>1500/mm³) or normal range, resume dosing at 200 mg BID. If the Grade 3 neutropenia persists, discontinue GDC-0853. Second occurrence of Grade 3 neutrophil count decreased: Withhold GDC-0853, recheck CBC in 7 days. If the
	neutrophil count has recovered to Grade 1 (>1500/mm³) or normal range, restart GDC-0853 at the lower dose of 200 mg QD. If the Grade 3 neutrophil count decreased persists, discontinue GDC-0853.
	Third occurrence of Grade 3 neutrophil count decreased: Discontinue GDC-0853.
Grade 4: ANC < 500/mm ³	For Grade 4 neutrophil count decreased: discontinue GDC-0853.
Thrombocytopenia ^d	
Grade 1: PLT > 75,000/mm ³	In the absence of bleeding event(s), maintain GDC-0853 dosing.
Grade 2: PLT 50,000-75,000/mm	First occurrence of Grade 2 platelet count decreased: withhold GDC-0853, recheck CBC in 7 days. If platelet count has recovered to Grade 1 or has returned to the normal range, and in the absence of bleeding resume dosing at 200 mg BID.
	Second occurrence of Grade 2 platelet count decreased: withhold GDC-0853, recheck CBC in 7 days. If platelet count has recovered to Grade 1 or has returned to the normal range and in the absence of bleeding restart GDC-0853 at the lower dose of 200mg QD.
	Third occurrence of Grade 2 platelet count decreased: Discontinue GDC-0853.

Table 3 Guidelines for Management of GDC-0853 in Patients Who Experience Specific Adverse Events (cont.)

Event	Action to Be Taken ^a
Grade ≥ 3: PLT < 50,000/mm ³	For Grade 3 or greater platelet count decreased: discontinue GDC-0853.
Gastrointestinal effects	
Nausea, vomiting, and/or diarrhea	Manage according to site institutional guidelines. Consider administration of GDC-0853 with food as possible mitigation strategy.
	Consider reducing GDC-0853 dose to 200 mg QD and discuss with Medical Monitor.
Malignancy	
Any malignancy (with the exception of non-serious local and resectable basal or squamous cell carcinoma of the skin).	Discontinue GDC-0853. Report event as an adverse event of special interest to the Sponsor in an expedited manner.
Hepatotoxicity	
Any AST or ALT $> 3.0-5.0 \times ULN$	Withhold GDC-0853 and consult with the Medical Monitor.
AST or ALT elevation >3×ULN in	Discontinue GDC-0853.

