combination with total bilirubin >2 × ULN, of which at least 35% is direct bilirubin, or clinical jaundice	Report event as adverse event of special interest to the Sponsor in an expedited manner.
Any AST or ALT $> 5 \times ULN$	Discontinue GDC-0853.
	Elevations of AST or ALT of $> 5 \times ULN$ should be reported as adverse event(s) of special interest to the Sponsor in an expedited manner.
Cardiovascular effects	
Sustained (at least two ECG measurements > 30 minutes apart) QTcF that is > 500 msec and/or > 60 msec longer than the baseline value	Unless there is a clear alternative cause other than study drug, discontinue GDC-0853 ^e

Table 3 Guidelines for Management of GDC-0853 in Patients Who Experience Specific Adverse Events (cont.)

Event	Action to Be Taken ^a
Sustained absolute QTcF that is > 515 msec	Unless there is a clear alternative cause other than study drug, discontinue GDC-0853 ^e
An episode of torsades de pointes or a new ECG finding of clinical concern	Unless there is a clear alternative cause other than study drug, discontinue GDC-0853 ^e
Vascular Inflammation	
Vasculitis	Consult with the Medical Monitor
Hypersensitivity reactions	
Fever, chills, pruritis, urticaria, angioedema, and skin rash	Treat patient according to the standard of care for management of anaphylaxis/anaphylactoid or a hypersensitivity reaction.
Cardiopulmonary reactions, including chest pain, dyspnea, hypotension, or hypertension	Discontinue GDC-0853.
Persistent gastrointestinal symptoms (e.g., crampy abdominal pain, vomiting)	

CBC = complete blood count; IV = intravenous; MTX = methotrexate; PLT = platelet count; ULN = upper limit of normal.

- ^a Any patient who discontinues GDC-0853 should enter safety follow-up if possible.
- b Appropriate laboratory investigations, including but not limited to cultures, should be performed to establish the etiology of any serious infection.
- ^c Patients withdrawn from the study because of a reduced neutrophil count must be followed closely for signs of infection, with treatment as deemed appropriate by the investigator, including discontinuation of MTX if indicated, and must have a repeat WBC count with differential performed weekly until the ANC is above 1000 cells/mm³ (1.0 × 10⁹/L) within 2 months (or sooner if deemed necessary by the investigator), a hematology referral is recommended.

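### Sections 1.3 and 5.1.1.8 stop study drug for vasculitis, but Table 3 says only to consult; the Day 84 first-dose instructions also conflict

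*Combined protocol and SAP*

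**What the plan says.** **Vasculitis.** Section 1.3 says: "Study drug should be discontinued in any patient who develops an adverse event of vasculitis, and the patient should enter the safety follow-up period". Section 5.1.1.8 repeats the rule as a risk-mitigation measure ("Study drug should be discontinued in any patient who develops an adverse event of vasculitis"), and its next paragraph adds: "Guidelines for management of GDC-0853 in the event of vasculitis in patients are provided in Table 3". The vascular inflammation row of Table 3 (Section 5.1.2) reads, in full, "Consult with the Medical Monitor". Section 4.5.2 opens its list with "Patients must discontinue study treatment if they experience any of the following" and names eight reasons. Vasculitis is not among them.

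**Day 84.** Section 4.2.2.1 and the synopsis say that "the last dose of GDC-0853 for Study GA29350 is the a.m. dose on Day 84 for all patients" and that "the first open-label dose of GDC-0853 should be the p.m. dose (may be taken at home) on Day 84". Appendix 1 differs. Footnote f tells patients not to take blinded drug on Day 84. Footnote m puts the last blinded dose on the evening before and the first open-label dose on the morning of Day 84.

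**The concern.** Table 3 is what a site is likely to open when an event occurs. Section 5.1.2 presents it as the guide to managing study drug for specific events, and Section 5.1.1.8 sends the reader there. If its vasculitis row omits the stop, a patient could stay on drug while a consultation is arranged, or after it, although the protocol's stated mitigation is to discontinue.

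The risk is one the protocol takes seriously. In the 4-week dog study, vascular inflammation appeared at 56 µM·h or more, had not fully reversed after a 4-week recovery, and did not track consistently with any clinical biomarker (Section 5.1.1.8). Laboratory monitoring may therefore give little warning. Section 1.3 calls the human risk uncertain. After Week 12, scheduled safety visits are about 12 weeks apart (Section 3.1). Vasculitis is also not an adverse event of special interest in Section 5.2.3, so a non-serious case carries no 24-hour report on that ground.

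The Day 84 conflict matters less. It affects whether that morning's drug is blinded or open-label and whether the first open-label dose is supervised. For patients coming from placebo or adalimumab, that dose is their first GDC-0853.

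**Working it through.** The check compares current protocol text; the summary of changes was not used. The plan gives no figure of its own to reproduce.

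**Vasculitis, source by source**

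| Place | Action on study drug |
|---|---|
| Section 1.3 | Discontinue, then safety follow-up |
| Section 5.1.1.8 | Discontinue, then safety follow-up; refers to Table 3 |
| Table 3, vascular inflammation row | None; consult only |
| Section 4.5.2 list | Vasculitis not listed |

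**Can the Table 3 row be read as shorthand for stopping?** No. For AST or ALT above 3 and up to 5 × ULN, the same table says "Withhold GDC-0853 and consult with the Medical Monitor". It pairs a hold with a consultation in the same way for serious bleeding. It says outright to discontinue for malignancy, AST or ALT above 5 × ULN, Grade 4 neutropenia and hypersensitivity. Where a dosing action is meant, the table states it.

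**Count of event classes in Table 3.** Infection, bleeding, neutropenia, thrombocytopenia, gastrointestinal effects, malignancy, hepatotoxicity, cardiovascular effects, vascular inflammation and hypersensitivity make 10. Classes with at least one dosing action (maintain, withhold, reduce or discontinue): 10 − 1 = 9. The exception is vascular inflammation.

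**Exposure context.** Section 3.3.1 anticipates a mean AUC0–24 below 10 µM·h.
- Against the 4-week dog effect level: 56 / 10 = 5.6, so the margin is more than 5.6-fold.
- Against the highest exposure without the finding in the 9-month dog study: 36 / 10 = 3.6, so the margin is more than 3.6-fold.

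**Day 84, source by source**

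| Place | Morning of Day 84 | First open-label dose |
|---|---|---|
| Synopsis; Section 4.2.2.1 | Last parent-study dose | Evening, may be at home |
| Appendix 1, footnote f | No blinded drug | Not stated |
| Appendix 1, footnote m | Open-label drug | Morning |
| Appendix 1, dosing footnote | Not stated whether blinded | Morning of Day 1 |
| Appendix 1, Week 0 in-clinic mark (carries footnote m) | Dose in clinic | In clinic |
| Appendix 1, PK footnote | In-clinic dose time recorded on Days 1 and 84 | Not stated |
| Figure 1 text, Section 3.1 | Week 0 morning dose in clinic | Implied morning |

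Footnotes f and m contradict Section 4.2.2.1 directly. The other Appendix 1 items and the Figure 1 text fit the morning, in-clinic start but do not all address blinded drug. Mixing the instructions has a practical cost. Footnote f followed by Section 4.2.2.1 leaves no morning dose; Section 4.2.2.1 followed by footnote m gives two.

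**Size of the Day 84 difference.** Planned open-label doses = 52 weeks × 7 days × 2 per day = 728. One dose is 1 / 728 = 0.14%.

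**The case against.** The strongest reply is that stopping and consulting are compatible. The stop instruction in Section 5.1.1.8 comes just before the pointer to Table 3, Section 4.2.2.1 sends sites to the whole of Section 5.1 and not to the table alone, and even a site using only Table 3 must call the Medical Monitor. That narrows the risk to sites that go straight to the table, but does not remove it: the row still lacks an action that two sections require.

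Several narrower points stand as limits:
- The omission from Section 4.5.2 is weak evidence. That list also lacks other events for which Table 3 says to discontinue: AST or ALT above 5 × ULN, AST or ALT above 3 × ULN with raised bilirubin or jaundice, and sustained QTcF prolongation. It is not a complete stopping list. The Table 3 row carries the argument.
- The count of 9 in 10 is generous, since it accepts maintaining dose, or considering a reduction, as a dosing action. It describes the table and measures no risk. The comparison with the AST/ALT row is enough.
- Sections 1.3 and 5.1.1.8 use advisory wording, whereas Section 4.5.2 is mandatory.
- The animal signal should be read in context: no drug-related vascular inflammation in the 9-month dog study up to 36 µM·h, anticipated clinical exposure below 10 µM·h, and Beagles prone to spontaneous polyarteritis.
- On Day 84, the visit sequence in Section 4.4.5 lists no assessments after in-clinic dosing, so supervision adds little monitoring.

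None of these reconciles the conflicting texts. They bear on how urgent the correction is.

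**Conclusion.** The concern holds; the plan is wrong as written on both points. For vasculitis, two sections say stop, the table they lead to says only consult, and the mandatory list is silent. A site using Table 3 alone would miss the stated stopping rule. The number of patients affected cannot be estimated, because the documents give no expected vasculitis rate.

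For Day 84, the instructions cannot both be followed. The difference is one dose in 728 (0.14%), negligible for total exposure; the documents do not say for how many patients it would be a first GDC-0853 dose.

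Both should be fixed in the next amendment, vasculitis first. The conclusion assumes that Sections 1.3 and 5.1.1.8 state the sponsor's intention. If consultation alone is intended, those sections need changing instead, and the mitigation they describe falls away.

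**What to change.** 1. Change the Table 3 vasculitis row to: discontinue GDC-0853, enter safety follow-up, and consult the Medical Monitor.
2. Add vasculitis to the Section 4.5.2 list. Since that list also lacks the liver and QTcF stops, a cross-reference to Table 3 would close the same gap for those events.
3. Give one Day 84 instruction throughout. Align Appendix 1 (footnotes f and m, the dosing and PK footnotes, and the Week 0 in-clinic mark) and the Figure 1 text with Section 4.2.2.1 and the synopsis. If the parent protocol stops blinded drug on Day 83, change Section 4.2.2.1 and the synopsis instead. The parent protocol must be checked before choosing.

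The cost is wording in the next amendment and a letter to sites. No new data, visits or patients are needed.
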